#### 4.2.6 Premature Discontinuation

Patients will discontinue the trial if any of the following are true:

- Participant requests to be withdrawn from trial; in this event, the reasons for withdrawal will be documented. If at all possible, the patient should return for the Post Treatment Follow-up Visit.
- A patient who is noncompliant with protocol guidelines may be removed from the trial at the discretion of the principal investigator.
- Disease progression, as described in Removal from Protocol Therapy [Section 4.2.5](#)
- Death.

#### 4.3 Trial Duration

The total duration of trial for each patient is up to 29 months

#### 4.4 Data and Safety Monitoring Board (DSMB)

The DSMB is a board that oversees the safety of patients participating in the trial. The primary responsibility of the DSMB is to review and evaluate the accumulated trial data for safety, trial conduct, and the integrity of the trial.

If an event occurs which fulfills the trial halting rules (see [Section 4.5](#) for further details) the DSMB will review the event in a timely manner and agree on a recommendation to halt, resume or terminate the trial participation of the affected patient(s) and/or the trial as a whole.

#### 4.5 Trial Halting Rules

A temporary halting or termination for the trial as a whole can be decided by the DSMB following the occurrence of:

- Unexpected (i.e. not listed in the current Investigator's Brochure) Grade 3 or higher systemic reaction or lab toxicity (using National Cancer Institute [NCI] Common Terminology Criteria for Adverse Events [CTCAE] version 4.03 or newer) with an at least reasonable possibility of a causal relationship to the administration of MVA-BN-Brachyury vaccine (i.e., the relationship to vaccine cannot be ruled out).
- Any unexpected SAE with a consequence of death

These parameters are not all-inclusive. Other AEs could occur that would trigger a safety review.

If an event fulfilling the trial halting criteria reaches the investigator's attention, the investigator has the liability to alert the BN Pharmacovigilance immediately (within 24 hours) and provide a comprehensive documentation of the event.

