## 1.4 Protocol Synopsis

Title	A Phase 2 Trial of BN-Brachyury and Radiation Therapy in Patients with Advanced Chordoma
Clinical phase	Phase 2
Sponsor	Bavarian Nordic A/S [REDACTED]
Principal Investigator	[REDACTED]
Number of sites	Minimum 4, Up to 10 (USA)
Vaccination dose, schedule and administration route	
Prime with Modified Vaccinia Ankara-Bavarian Nordic (MVA-BN)-Brachyury given subcutaneously (SC) for one dose each on Day 0 and Day 14. Administer each dose as four separate 0.5 mL injections (for a total dose of at least <math>5 \times 10^7</math> Inf.U) one in each arm, one in each leg using professional standards and practices.
 
Boost with Fowlpox Virus (FPV) -Brachyury given SC on Day 28, then every 4 weeks for 4 doses (End of Radiation +2, 6, 10, and 14 weeks), then given every 12 weeks (End of Radiation +26, 38, 50, 62, 74, 86, 98, and 110 weeks). One dose = one 0.5 mL injection with a nominal titer of <math>1 \times 10^9</math> Inf.U per 0.5 mL.

Trial duration	The total duration of the trial for each patient is up to 29 months
Trial population	Patients at least 12 years old with advanced chordoma who are planning to be treated with radiotherapy to at least one lesion. Patients will have no history of autoimmune disease (with exceptions detailed in the exclusion criteria below), will have measurable disease as defined by Response Evaluation Criteria in Solid Tumors (RECIST) 1.1, and will have adequate organ function
Number of patients	Planned trial size is based on a Simon 2-stage design, in which 10 patients are treated initially. If $\geq 1$ patient(s) in the first 10 have an objective response [partial response (PR) or complete response (CR)] by RECIST 1.1, an additional 19 patients may be enrolled for a total of 29 patients. Otherwise, the trial will be stopped. If 4 or more objective responses are observed in 29 patients, the null hypothesis that the true Objective Radiographic Response Rate (ORR) anytime within 12 months post completion of radiation is 5% or less will be rejected. This

design yields a one-sided type I error rate of 5% and power of 80% when the true response rate is 20%.

---

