### 4.2 Description of Trial Procedure

Patients will be treated with 2 priming doses of MVA-BN-Brachyury (Doses 1 and 2) and 1 dose of FPV-Brachyury (Dose 3) prior to initiation of radiotherapy. MVA-BN-Brachyury will be administered on Day 0 and approximately Day 14 (+ / - 2 days) followed by FPV-Brachyury on approximately Day 28 (+ / - 2 days). Radiotherapy will begin at least 2 weeks and not more than 4 weeks after first administration of FPV-Brachyury (Dose 3). Radiotherapy will proceed according to the dose and schedule selected by the treating radiation oncologist with guidelines detailed in [Section 6.3.1.2](#). The trial team must collect documentation of the dose and schedule of radiotherapy administered. The dose and schedule must comply with radiotherapy minimum requirements as defined in [Section 6.3.1](#).

At least 2 weeks following completion of radiotherapy (or upon resolution of any reversible AEs related to radiotherapy to Grade 1 or baseline if ongoing beyond 2 weeks), the patient will resume vaccination with FPV-Brachyury (Dose 4) and proceed to ongoing booster doses with FPV-Brachyury at 4-week intervals until 4 booster doses with FPV-Brachyury have been administered (Doses 4, 5, 6, 7). Subsequent vaccine doses will be administered in 12-week intervals through

approximately 2 years beyond completion of radiotherapy (Doses 8, 9, 10, 11, 12, 13). A final visit will occur 30 days after the last treatment visit.

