## 9.5.2 Reporting of SAEs

Any SAE that occurs after the patient signs informed consent and until 30 days following administration of the last dose of trial product, irrespective of the treatment received by the patient, must be reported to BN within 24 hours of the investigative site learning of the event. All SAEs (initial and Follow-up information) will be reported to BN within 24 hours of the discovery of the event or information. SAE report forms will be available in electronic format as part of the eCRF. Manual, paper-based SAE report forms will be available as a backup process for the case of failure of electronic systems. BN or designee may request Follow-up and other additional information from the Investigator (e.g., hospital admission/discharge notes and laboratory results). Discharge summary at minimum will be requested for any hospitalization.

*The investigator should not delay reporting because of missing information. Nonetheless, the report should be as complete as possible.* This initial notification should include, at a minimum, sufficient information to permit identification of the following:

- The reporter (investigator's name and contact information)
- The patient
- Involved trial medication/vaccine
- AE(s)
- Seriousness criterion
- Date of onset
- Investigator assessment of causality

If trial drug vaccine is discontinued because of an SAE, this information must be included in the SAE report.

Investigators must report SAEs to their governing IRBs in writing as soon as possible and in accordance with national and local laws and regulations.

Periodic reporting is the responsibility of BN.

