## 3.4.4.2 AE Causality

The relationship between the occurrence of an AE and the trial treatment will be assessed using the categories "none," "unlikely," "possible," "probable," and "definite." This assessment is applied to each trial product (MVA-BN-Brachyury, FPV-Brachyury, and Radiation) individually. For assessing related AEs in analyses, if the relationship of any of the products is considered possible, probable, or definite, the AE will be considered related to trial treatment. In the event of a missing causality, the AE will be classified as related.

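### The first halting criterion names only MVA-BN-Brachyury, so a non-fatal unexpected Grade 3+ reaction attributed only to FPV-Brachyury triggers no mandatory DSMB review

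*Protocol*

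**What the plan says.** Protocol Section 4.5 says the DSMB can decide on a temporary halt or termination after either of two events:

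- an unexpected Grade 3 or higher systemic reaction or laboratory toxicity with at least a reasonable possibility of a "causal relationship to the administration of MVA-BN-Brachyury vaccine". A parenthesis explains this as a relationship to vaccine that cannot be excluded;
- any unexpected SAE that results in death, whatever the product.

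It then adds: "These parameters are not all-inclusive. Other AEs could occur that would trigger a safety review".

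Two duties depend on these criteria. Section 4.4 begins its review duty with "If an event occurs which fulfills the trial halting rules" and says the DSMB will then review the event and make a recommendation. Section 4.5 requires the investigator to alert the sponsor's pharmacovigilance group within 24 hours and opens that duty with "If an event fulfilling the trial halting criteria reaches".

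On causality, SAP Section 3.4.4.2 says: "This assessment is applied to each trial product (MVA-BN-Brachyury, FPV-Brachyury, and Radiation) individually".

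**The concern.** The trial gives two investigational vaccines, and the first halting criterion names one of them. The one left out is the boost, which is given far more often and over a much longer time. If sites and the sponsor follow the rule as written, a serious-grade but non-fatal surprise attributed to the boost alone does not oblige the DSMB to look at it. What is at stake is the guarantee of prompt independent review for that class of event. The DSMB keeps its power to act.

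**Working it through.** No figure in the plan needs reproducing here. The check is a reading of the rule against the rest of the text, with some simple counting.

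**1. Are these separate products?** Yes. Protocol Section 2.5.2 describes two different viral vectors and uses BN-Brachyury as the joint name. Section 6 gives each its own product description and titer. Where the protocol means both, it can say so: the full analysis set in Section 10.4.1 is defined by a dose of either one. Criterion 1 uses neither the joint name nor both names.

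**2. Can an event be attributed to FPV-Brachyury alone?** Yes. The SAP has causality rated for each product individually. MVA-BN-Brachyury is given on Day 0 and Day 14 only, while FPV-Brachyury continues to 110 weeks after radiation in the synopsis, so excluding the prime becomes easier at later boosters.

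**3. How much of the schedule is FPV-Brachyury?**

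- Synopsis: MVA-BN-Brachyury 2. FPV-Brachyury 1 (Day 28) + 4 (End of Radiation +2, 6, 10, 14 weeks) + 8 ("then given every 12 weeks (End of Radiation +26, 38, 50, 62, 74, 86, 98, and 110 weeks") = 13. Total 2 + 13 = 15; 13/15 = 86.7%.
- Section 4.2: MVA-BN-Brachyury 2 (Doses 1 and 2). FPV-Brachyury 1 (Dose 3) + 4 (Doses 4 to 7) + 6 ("approximately 2 years beyond completion of radiotherapy (Doses 8, 9, 10, 11, 12, 13") = 11. Total 2 + 11 = 13; 11/13 = 84.6%.

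The two places disagree on the number of boosters, which is a separate matter; the conclusion is the same under both. These counts show which product is omitted. They are not a share of risk.

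**4. What happens to each type of unexpected, Grade 3 or higher, systemic or laboratory event?**

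| Event | Listed halting criterion met? | DSMB review required by Section 4.4? | Stated timeline to sponsor |
|---|---|---|---|
| Possibly related to MVA-BN-Brachyury, or MVA-BN-Brachyury cannot be ruled out | Yes, criterion 1 | Yes | 24 hours |
| Fatal SAE, any product | Yes, criterion 2 | Yes | 24 hours |
| FPV-Brachyury only, non-fatal, SAE or AESI | No | No | 24 hours (Sections 9.5.2 and 9.5.3) |
| FPV-Brachyury only, non-fatal, not an SAE or AESI | No | No | eCRF within 5 days of the visit (Section 13.1) |

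In the third row the event "must be reported to BN within 24 hours of the investigative site learning of the event", but that section sends it to the sponsor and does not require DSMB review. In the fourth row the two clocks start at different points: the alert runs from the investigator's awareness, the eCRF deadline from the visit.

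**5. Does other text fill the last two rows?** Section 4.2.5 stops vaccination for an individual patient after certain reactions attributed to vaccine generally, but it sends nothing to the DSMB. The general oversight role in Section 4.4 and SAP Section 3.6 lets the DSMB act on safety information without obliging it to review a given event. No passage extends criterion 1 to FPV-Brachyury.

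**The case against.** The strongest reply is that the rule is probably meant to cover both vaccines. The parenthesis in criterion 1 speaks of vaccine without naming a product, and the protocol elsewhere uses that word for the whole regimen (Section 4.2.5, and the dosing-delay text in Section 6). That reading is possible. However, the parenthesis is introduced as a restatement of the MVA-BN-Brachyury condition, so it does not clearly widen it. A safety rule that can be read either way needs the same edit.

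Second, the threshold is low. The schedule gives both MVA-BN-Brachyury doses before any FPV-Brachyury, and both vectors carry the same transgenes, so an investigator must positively exclude the prime before an event leaves criterion 1. This stands as a real limit. It makes the gap small around Day 28 and for immune reactions to the shared transgenes, and less so for an acute reaction to a late booster.

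Third, per-product causality is stated in the SAP, and the same section pools products when counting related events. That is also true. But the pooling governs the analysis tables and does not change the halting rule.

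Fourth, other safeguards overlap. Immune-mediated events after first MVA-BN-Brachyury exposure are AESIs throughout the booster phase, important medical events count as serious, and the list of criteria is expressly open-ended. These stand too, and they are why the gap is narrow. None of them makes DSMB review mandatory. Finally, even a met criterion only allows a halt, so what is lost is the assured review and not the authority to stop.

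**Conclusion.** The concern holds, within narrow bounds. As written, a non-fatal, unexpected Grade 3 or higher systemic reaction or laboratory toxicity attributed only to FPV-Brachyury meets no listed halting criterion, so DSMB review of it is optional. If it is also non-serious and not an AESI, the stated timeline is 5 days from the visit in place of 24 hours from awareness.

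This rests on reading criterion 1 literally and on investigators attributing events product by product. The documents give no rate for such events, so how often the gap would matter cannot be estimated. Nothing in the plan gives a reason for leaving FPV-Brachyury out, and it may be a drafting omission. It should be corrected because it sits in a stated safety rule; it does not by itself show that patients are at greater risk.

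**What to change.** In the first criterion of Protocol Section 4.5, replace the single product name with MVA-BN-Brachyury or FPV-Brachyury. The vaccinations named by the criterion then rise from 2 of 15 to 15 of 15 on the synopsis schedule, or from 2 of 13 to 13 of 13 on the Section 4.2 numbering. The Section 4.4 review and the 24-hour alert both refer back to the halting criteria, so they follow without further edits.

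The cost is one product name in one line of protocol text, with no new data collection.

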## 5 Selection of Patients

### 5.1 Recruitment Procedure

This trial will be listed on available websites (<http://www.clinicaltrials.gov>, [www.cancer.gov/clinicaltrials](http://www.cancer.gov/clinicaltrials), <http://clinicalstudies.info.nih.gov>) and participants will be recruited from the current patient population at the site.

### 5.2 Inclusion Criteria

A subject will be eligible for inclusion in this trial if ALL of the inclusion criteria apply. Refer to Trial Synopsis ([Section 1.4](#)).

### 5.3 Exclusion Criteria

A subject will not be eligible for inclusion in this trial if ANY of the exclusion criteria apply. Refer to Trial Synopsis ([Section 1.4](#)).

## 6 Investigational Medicinal Product

### MVA-BN-Brachyury

- MVA-BN-Brachyury vaccine is a liquid-frozen, highly attenuated, live recombinant virus based on the viral vector MVA-BN. It is administered as subcutaneous application.
- One MVA-BN-Brachyury vaccine vial has a nominal virus titer of at least  $2.5 \times 10^7$  Inf.U per 0.5 mL of the drug product. The specific dose will be determined upon release testing of the drug product.
- For further details on the MVA-BN-Brachyury vaccine, see current version of the Brachyury Investigator's Brochure.

### FPV-Brachyury

- FPV-Brachyury is a liquid-frozen, highly attenuated, live recombinant virus. It is administered as subcutaneous application.
- One FPV-Brachyury vial has a nominal virus titer of  $1 \times 10^9$  Inf.U in 0.5 mL of the drug product. The specific dose will be determined upon release testing of the drug product.
- For further details on the FPV-Brachyury vaccine, see current version of the Brachyury Investigator's Brochure.

No dose modifications will be allowed on this trial. Any patient who experiences a dose limiting toxicity or allergic or autoimmune toxicity as defined in [Section 4.2.5](#) will not receive any additional vaccinations.

[figure not shown]
If a scheduled dose of the vaccine is missed, the vaccine may be given within the treatment window specified in [Section 1.5](#). If the patient has a delay in vaccination not due to toxicity, the vaccine may be delayed for up to 42 days without removal of the patient from trial.

**Dosing Delay:** Patients should have resolution to  $\leq$  Grade 1 or return to baseline of all toxicities prior to the start of the next injection of the vaccine. If  $>$  Grade 2 toxicity attributed to vaccine persists for  $>$  28 days, the patient will not receive further vaccine injections and will be removed from vaccine therapy.

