Medical assessments include a complete neurologic examination including documentation of cranial nerve, motor, sensory, cerebellar, and deep tendon reflex examinations; interim history (since last visit); vital signs; physical examination (at baseline); targeted physical exam (Day 0-28, End of Radiation +2-+110 weeks, and Post-treatment follow up visits) and ECOG performance status. To be performed within 3 days prior of each dose of vaccine. Repeat medical assessment is not required at baseline if history and physical has been performed within 3 days of vaccine administration on day 0.

Serum HIV antibody should be completed within 6 months of initiating treatment.

Serum hepatitis B & C antibody should be completed within 6 months of initiating treatment.

Chemistry panel: Na+, K+, Cl, CO2, glucose, (BUN), creatinine, albumin, alkaline phosphatase, ALT, AST, total bilirubin, thyroid stimulating hormone (TSH), calcium, and ANA to be performed within 16 days prior to screening/ baseline per protocol. TSH is optional after screening visit.

In females of child-bearing potential, Beta-HCG to be done at baseline 48 hours prior to treatment and within 48 hours of any dose of vaccine or radiation.

CT chest, abdomen, and pelvis and MRI (if target lesion is best visualized by MRI)

Correlative biomarker studies (blood): 6 (10 mL) green top sodium heparin tubes for PBMC; 1 (8.5 mL) SST tubes for serum samples.

Radiotherapy schedule and dose selected by treating radiation oncologist. Radiotherapy will begin at least 2 weeks and ideally not more than 4 weeks after first administration of FPV-Brachyury (Dose 3).

 RECIST based assessment includes using RECIST principles (see [Section 10.5](#)) to measure the “target” lesions, defined as those meeting RECIST requirements for measurability and those that will be treated with radiation as defined by minimum requirements of the protocol. “Non-target” lesions may include those that are not measurable by RECIST or those that are measurable and not treated with radiotherapy at the dose required by protocol (per [Section 6.3.1](#)).

Time noted is from end of radiation or until resolution of AEs related to radiation, whichever is later

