### 4.2.2.2 Evaluation of Response

Appropriate imaging with CT of the chest/abdomen/pelvis and MRI (if target lesion is best visualized by MRI) to reassess tumor extent and to determine tumor measurements will be performed 14 weeks after completion of radiotherapy and with each subsequent dose of vaccine thereafter (with windows for treatment as designated in the schedule of events, [Section 1.5](#)).

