## **9.4 CT Scan**

A CT scan of the thorax, abdomen and pelvis will be done as described in [Section 1.5](#) to assess tumor response. Screening scans are only acceptable if they are acquired within 28 days of the first dose. CT scans acquired during the treatment period have an allowable clinic visit window of  $\pm 1$  week. Image consistency is essential to allow comparisons of scans over time. At each site the same equipment and scanning parameters should be used throughout the trial. IV contrast is recommended except in cases where it is medically contraindicated.

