### 10.2 Endpoints

#### Primary endpoints:

- ORR anytime within 12 months post completion of radiation on target lesion(s) based on modified RECIST 1.1. Refer to [Section 10.5](#) for the response criteria.

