Standard RECIST 1.1 evaluations based on all lesions will be performed by external radiological reviewers and results will be included in exploratory analyses.

Each patient will be assigned one of the following categories: 1) CR; 2) PR; 3) SD; 4) progressive disease; and 5) not evaluable (death prior to restaging from malignant disease, toxicity, or due to other causes; or insufficient data). Patients will be assessed at fixed intervals as indicated by the schedule of events ([Section 1.5](#)).

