#### 3.5.3.3.1 Additional Analyses of the Primary Efficacy Endpoint

Baseline tumor measurements will be taken during the screening period. Objective tumor responses will be assessed every 3 months starting approximately 14 weeks after radiation therapy. Besides ORR based on the best post-treatment tumor assessment within 12 months after radiation therapy and during the trial, ORR will also be summarized for the EAS by visits with scheduled tumor assessments.

Best post-treatment tumor responses within 12 months after radiation therapy and during the trial by mRECIST will also be summarized for the EAS by location of primary tumor and histologic subtype (refer to subgroups summarized in Section 3.3), and for the FAS as a sensitivity analysis. For sensitivity analyses based on the FAS, subjects without post-treatment tumor assessments will be analyzed as non-responders (regardless of survival status) for OR endpoints.

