**BRACHY-CHOR-001** 

provided to the DSMB for benefit-risk assessment and for confirmation of tumor response. The DSMB may recommend to temporarily halt or terminate the trial based on safety information.

Stage 2 OR assessments will be reviewed continuously, once all subjects accrued have completed at least two post-baseline CT or MRI scans for tumor assessment. Because ORR may increase with further follow up, ORs will be followed until all subjects have reached the 12 months post-radiation time point or progressed. For subjects who have completed multiple scans, the best OR within 12 months after radiation therapy will be used.

Final analysis will occur when all of the subjects accrued have either completed the 2-year treatment period or have progressed.

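### After week 14 the protocol ties response scans both to the vaccine dose and to the visit window. If the dose is late and the scan follows it, the week-50 scan can fall outside the 12-month primary endpoint

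*Protocol*

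**What the plan says.** **Endpoint.** Protocol Section 10.2 defines the primary endpoint as "ORR anytime within 12 months post completion of radiation on target lesion(s) based on modified RECIST 1.1". SAP 3.6 says that for patients with several scans "the best OR within 12 months after radiation therapy will be used".

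**Scan timing tied to the dose.** Protocol Section 4.2.2.2 puts the first scan 14 weeks after radiotherapy and later scans "with each subsequent dose of vaccine thereafter (with windows for treatment as designated in the schedule of events", that is, Section 1.5.

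**Scan timing tied to the calendar.** The Section 1.5 table marks CT/MRI at weeks 14, 26, 38, 50 and later after the end of radiation, with a ±2-week window from week 26. Section 10.5 says "Patients will be assessed at fixed intervals as indicated by the schedule of events". SAP 3.5.3.3.1 says "Objective tumor responses will be assessed every 3 months starting approximately 14 weeks after radiation therapy".

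**Dose delay.** Section 6 (FPV-Brachyury) first lets a missed dose be given inside its Section 1.5 window. It then allows more: "If the patient has a delay in vaccination not due to toxicity, the vaccine may be delayed for up to 42 days without removal".

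**Restart after radiation.** Under Section 4.2, Dose 4 is given at least 2 weeks after radiotherapy, or once reversible radiation adverse events (AEs) have settled if they last longer. Later doses follow at 4-week and then 12-week intervals. Footnote 11 of Section 1.5, attached to the first post-radiation column, reads: "Time noted is from end of radiation or until resolution of AEs related to radiation, whichever is later".

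**The concern.** For a dose given on time, the two scan rules agree. For a dose given outside its window, they cannot both be met: the scan is either with the dose or in the window. The 42-day allowance is three times the half-width of the window, so the protocol itself permits this situation. Neither document says what then happens to the scan.

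Week 50 is where it matters, because it is the last scheduled scan before the 12-month limit. A patient whose week-50 scan moves past the limit has one fewer chance to be counted as a responder, for a reason unrelated to the tumor. Protocol Section 10.4.3 expects the response rate to rise with follow-up, so the last scan is not idle. Success needs 4 responses in 29 patients, so one uncounted response can change the result. The best response over the whole trial, also planned in SAP 3.5.3.3.1, would show a late response but does not enter the test.

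Affected patients stay in the primary analysis. The evaluable set asks for 3 of 4 boosters in the 14 weeks after radiation, and a late week-50 dose does not touch that rule.

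**Working it through.** **Inputs.** Scan weeks, windows and footnote 11: Protocol Section 1.5. Delay of up to 42 days: Section 6. Dose 4 rule and dose intervals: Section 4.2. Design (10 then 29 patients; continue on ≥1 response, reject on ≥4; 5% against 20%): Section 10.3. Assumptions: 12 months = 365 days, and the delay is counted from the nominal date.

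**1. The plan's own figures.** With X₁ ~ Bin(10, p) and X₂ ~ Bin(19, p), P(reject) = Σ over x = 1 to 10 of P(X₁ = x)·P(X₂ ≥ 4 − x).
- p = 0.05: type I error 0.0468; early stopping 0.95¹⁰ = 0.599; expected size 10 + 0.401 × 19 = 17.6.
- p = 0.20: power 0.801.

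All agree with Section 10.3.

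**2. Scan kept on the calendar.** Nominal days are 7 × 14 = 98, 7 × 26 = 182, 7 × 38 = 266 and 7 × 50 = 350. With ±14 days, week 50 falls on day 336 to 364. All four scans are inside 365 days.

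**3. Scan follows a late dose.** The week-50 scan is at day 350 + d. It passes day 365 when d ≥ 16, and d = 42 gives day 392. So d = 16 to 42 gives day 366 to 392, and the in-window scans are days 98, 182 and 266: three. Taking 12 months as 364.8 or 366 days moves the threshold to 15 or 17 days. A week-38 dose 42 days late is at day 308, still inside.

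**4. Late restart after radiation AEs.** Let k be the day on which the AEs resolve. Under Section 4.2, Dose 4 is at max(14, k). If later doses keep their intervals, the week-50 dose is 350 − 14 = 336 days after Dose 4.
- Nominal: 336 + k > 365 when k ≥ 30.
- Late edge of the window: 350 + k > 365 when k ≥ 16.

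The first scan stays at 14 weeks after radiotherapy. With k = 30 and later scans following the doses, scans fall at days 98, 198, 282 and 366: three in-window. The first three boosters are then at days k, k + 28 and k + 56, all by day 98 if k ≤ 42. A patient with k from 30 to 42 therefore still meets the booster rule of the evaluable set.

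**5. Illustration of size.** The documents give neither f, the share of responders first seen at week 50, nor q, the share of patients whose week-50 scan is late. Assume a true rate of 20%, the same reduced rate 0.20 × (1 − f·q) in both stages, and that a confirmatory scan may fall after month 12.

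| f | q | rate | power | loss (points) |
|---|---|---|---|---|
| 10% | 10% | 0.198 | 0.795 | 0.6 |
| 10% | 20% | 0.196 | 0.788 | 1.3 |
| 10% | 30% | 0.194 | 0.782 | 2.0 |
| 25% | 10% | 0.195 | 0.785 | 1.6 |
| 25% | 20% | 0.190 | 0.768 | 3.3 |
| 25% | 30% | 0.185 | 0.749 | 5.2 |

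At a true rate of 5%, lost responses only lower the counted rate, so type I error stays at 0.0468 or less.

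**The case against.** The strongest reply is that the documents already settle the matter in favor of the calendar. Section 4.2.2.2 carries its own limit to the Section 1.5 windows, which puts the week-50 scan at day 364 at the latest. Section 10.5 and SAP 3.5.3.3.1 describe fixed spacing. Section 9.4 is tighter still: "CT scans acquired during the treatment period have an allowable clinic visit window of" ±1 week, or day 343 to 357. The 42-day sentence concerns removal from trial and does not mention imaging. This stands as far as it goes. A reader might infer that the protocol moves the scan to as late as day 392; the documents do not say so. But the same sentence of Section 4.2.2.2 also ties the scan to the dose, and for a dose outside its window a site has no rule for choosing between the two.

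On the restart route, a reader might take footnote 11 to move every visit day for day with AE resolution, so that AEs settling on day 16 (or day 2 at the window edge) would be enough. Section 4.2 does not support that: AEs settled by day 14 move nothing, which gives the thresholds of about day 30 and day 16. The first scan does not move either, since Section 4.2.2.2 counts it from completion of radiotherapy.

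The size is assumed. SAP Section 4 mentions a few early responses in stage 2, which gives no support to a large share first seen at week 50. The SAP is dated November 2021 with stage 2 responses under review, so new scan instructions may come too late for many patients.

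**Conclusion.** The concern holds as an unresolved conflict between two scan-timing rules, with a definite consequence if a site follows the dose: a week-50 scan at day 366 to 392 and three in-window scans instead of four. A vaccine restart at about day 30 or later after radiation (about day 16 at the late window edge) can do the same, provided that later doses keep their intervals and scans follow them.

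The direction is against the treatment. The overall size cannot be derived from the documents. The illustrated loss of about 0.6 to 5.2 power points, from 0.801, depends on the assumed f and q, and its upper end needs both to be high.

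Two further inferences are not supported. A reader might add the power lost if stage 1 is decided after two scans, before week 50; that loss would occur with no delay at all and is a separate matter. A reader might also argue that a response first seen at week 50 can never count because its confirmation falls after 12 months; the documents do not require confirmation within that limit.

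**What to change.** Two short protocol edits:

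- **Section 4.2.2.2:** *Response scans are done 14, 26, 38 and 50 weeks after completion of radiation, then every 12 weeks, within the Section 1.5 windows, whether or not a vaccine dose is delayed.*
- **Section 1.5, footnote 11:** add *The later start applies to vaccine doses only; response scans are timed from completion of radiation.*

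The week-50 scan then falls at 350 + 14 = day 364 or earlier. Dosing rules, the evaluable set, the 12-month limit and the decision rule stay as they are. The cost is an occasional separate scan visit when a dose is late.

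Optionally, for scans already taken, SAP 3.5.3.3.1 could add a count of patients by number of response scans within 12 months after completion of radiation. It would use dates already collected and show whether the problem occurred.
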